7.3 Discussion of Study Design, Including the Choice of Control Groups

Intuvax is developed as an immune primer for cancer treatment that preferably should be combined with a drug that acts in synergy with Intuvax by inhibiting tumor-induced immunosuppression. In this study, Intuvax is given in combination with sunitinib, which like several other TKIs is known to inhibit myeloid-derived suppressor cells [25]. Based on current ESMO and NCCN guidelines [26, 27, 28] today's standard of care both in US and in the majority of the European countries involves initiation of systemic treatment with a TKI (including sunitinib or pazopanib) approximately 6 weeks post nephrectomy for all patients regardless of prognosis, i.e. poor (high risk) or intermediate. It is anticipated that all patients will benefit more from vaccination with Intuvax the sooner TKI treatment is initiated after performed nephrectomy.

Sunitinib alone was chosen as the active control for the study based on its documented positive impact on tumor response, PFS and OS in patients with mRCC. As discussed in *Section 5.2* it is hypothesized that sunitinib might contribute to an increased Intuvax efficacy.

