1 INTRODUCTION

This Statistical Analysis Plan (SAP) is based on Clinical Study Protocol (CSP) Version 9.0 dated 12 February 2019 (and Version 9.1 dated 19 February 2019 for France). It should be noted that, prior to protocol version 4.0, the trial design was different for intermediate risk patients, which leads to some specific considerations to be taken for subjects included in the trial corresponding to these versions.

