2 STUDY OBJECTIVES

The primary objectives are:

- To evaluate median overall Survival (OS) from randomization in metastatic renal cell carcinoma (mRCC) patients overall and by subgroup, i.e. in high-risk and in intermediate-risk patients separately, receiving two (2) vaccine doses of Intuvax pre-nephrectomy, followed by sunitinib initiated five (5) to eight (8) weeks post-nephrectomy and in non-vaccinated mRCC patients receiving sunitinib initiated five (5) to eight (8) weeks post nephrectomy
- To evaluate 18-month survival rate from randomization in mRCC patients overall and by subgroup, i.e. in high-risk and in intermediate-risk patients separately, receiving two (2) vaccine doses of Intuvax pre-nephrectomy followed by sunitinib post-nephrectomy and in non-vaccinated patients receiving sunitinib post-nephrectomy

The secondary objectives are:

- To evaluate safety and tolerability in high- and intermediate-risk mRCC patients receiving two (2) vaccine doses of Intuvax pre-nephrectomy followed by sunitinib post-nephrectomy and in non-vaccinated patients receiving sunitinib post nephrectomy
- To evaluate progression free survival (PFS) according to Response Evaluation Criteria In Solid Tumors (RECIST) 1.1 criteria from Sunitinib Start Visit in intermediate- and high-risk mRCC patients after receiving two (2) vaccine doses of Intuvax pre-nephrectomy followed by sunitinib post-nephrectomy and in non-vaccinated patients receiving sunitinib post nephrectomy
- To evaluate response and its duration according to RECIST 1.1 criteria from Sunitinib Start Visit in intermediate- and high-risk mRCC patients receiving two (2) vaccine doses of Intuvax pre nephrectomy followed by sunitinib post-nephrectomy and in non-vaccinated patients receiving sunitinib post-nephrectomy
- To evaluate time to tumor progression (TTP) from Sunitinib Start Visit in intermediate- and high-risk mRCC patients receiving two (2) vaccine doses of Intuvax pre-nephrectomy followed by sunitinib post-nephrectomy and in non-vaccinated patients receiving sunitinib post-nephrectomy
- To evaluate the number of infiltrating CD8+ T-cells in available diagnostic pre-biopsy (sample from either primary tumor or metastasis acceptable) and in the resected primary renal tumor in intermediate- and high-risk mRCC patients receiving two (2) vaccine doses of Intuvax pre-nephrectomy and in non-vaccinated patients

- [REDACTED]
- [REDACTED]
- [REDACTED]
- [REDACTED]
- [REDACTED]
- [REDACTED]
- [REDACTED]

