- Sunitinib Start Visit (Sun-Start), five (5) to eight (8) weeks after Nephrectomy
- Sunitinib Follow-up Visits (SFU[6W] and SFU[12W]), every 6 weeks for 12 weeks or until locally CT-verified PD whichever occurs first
- Sunitinib Follow-up Visits (SFU[24W], SFU[36W], SFU[48W], and SFU[60W]), every 12 weeks until End-of study or until locally CT-verified PD whichever occurs first
- End-of-Study Visit (End-of-Study)

The above described visits are applicable to all randomized subjects after and including protocol version 4.0. Subjects entering the trial corresponding to protocol versions prior to this, were included following a visit pattern that was different for high and intermediate risk patients. Following this design intermediate risk subjects would only start sunitinib treatment after confirmed PD.

At the two (2) Vaccination Visits, the patients are be administered Intuvax (10 x10⁶ DCs) intratumorally in the viable part of their primary tumor. Vaccine from the same batch (i.e. the same donor) is be used at both occasions. The patient stay at the clinic at least four (4) hours after vaccination. Nephrectomy is done at least 3 days after the second vaccination and maximum 63 days after Screening. Sunitinib treatment is initiated five (5) to eight (8) weeks after nephrectomy, administered dose is in accordance with the SmPC/USPI.

All patients are encouraged to contact the clinic in between study visits if they experience adverse events (AEs) or have any concerns. If follow-up of any symptoms is needed between the planned visits, the patient are scheduled for a visit as soon as possible and applicable assessments are performed.

A diagram of the study design is provided in Figure 1, and a flow chart what all assessments to be conducted per visit are provided in Tables 1 and 2.

Post-study survival data (either patient alive or date of death) will be collected.

[figure not shown]

Figure 1 Overall Study Design

Table 1 Study Flow Chart

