6.3.5 Primary Efficacy analysis

This is a descriptive proof of concept study and the sample size is not determined based on a statistical power calculation. Even though the trial is descriptive, some exploratory statistical testing will be conducted for primary endpoint, as described below.

Overall Survival

The primary endpoint is median OS, where OS is defined as the time from randomization to the time of death from any cause.

Median OS after randomization in high-risk and intermediate-risk mRCC patients will be calculated and compared overall and by subgroup based on FAS in the following way:

After the last patient has completed the trial, a collection of survival status, for patients still alive when exiting the study will be conducted by [REDACTED] Drug Safety. Additional collections will be conducted up to 5 years after collection of the last patient's 18 months survival data. For patients who die before end of trial, or patients with a known date of death during the additional collection, the survival time will be calculated as the difference in date of death and randomization date plus 1 day. Patients still alive at last contact, either during the trial or at the additional collection, will be censored at last date patient is known alive. Patients that are lost to follow-up during trial, or alive at end of trial where no follow-up information is available will be censored at last date patient is known alive.

Survival functions will be displayed graphically using Kaplan-Meier plots, and life table statistics will be produced including summaries of number of events and censored observations. Estimates of 25%, 50% (median) and 75% percentiles of time of survival with corresponding 95% confidence intervals will be calculated. Additionally, analyses where the survival functions will be compared between Intuvax+sunitinib, vs. sunitinib alone will be conducted using a stratified log-rank test, controlling for strata (high/intermediate-risk patients).

The analyses will be done overall, and separately for high/intermediate risk group of patients.

In addition, the primary efficacy endpoint will be evaluated using the PPS.

The analyses will be conducted using Proc Lifetest, SAS®.

18-month survival rate

18-month survival rate is defined as the proportion of patients alive 18 months after randomization, or probability of surviving beyond 18 months after randomization.

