6.3.6 Secondary Efficacy Analyses

PFS from start of sunitinib according to RECIST 1.1

PFS from start of sunitinib treatment will be derived as date whichever occurred first of any cause of death or date for first tumor progression (which is date for centrally assessed CT performed, according to RECIST 1.1) minus date for start of sunitinib treatment plus 1 day.

For the analysis of PFS only deaths occurring before end-of-trial will be accounted for in the analysis.

Analysis of PFS will be evaluated the following way:

Survival functions will be displayed graphically using Kaplan-Meier plots, and life table statistics will be produced including summaries of number of events and censored observations. Estimates of cumulative 25%, 50% (median) and 75% percentiles of survival with corresponding 95% confidence intervals will be calculated.

Comparison between Intuvax+sunitinib, vs. sunitinib alone will be done using a stratified log-rank test (controlling for strata intermediate/high risk), separate analyses will also be done by strata.

With protocol versions before version 4.0, intermediate risk patients did not have to initiate treatment with sunitinib at a fixed time point according to the visit schedule. Consequently some patients were never started on sunitinib, and in some cases sunitinib treatment was initiated at a later time point. The sunitinib start date constitutes the baseline time point for PFS according to protocol version 4.0 and after. In the analyses, patients who either had a delay or never started sunitinib will be included under the assumption that sunitinib treatment would have been initiated according to the final design, the date of the visit following the nephrectomy visit will be used as baseline.

Another issue that will be considered in the analysis is that some patients may have been discontinued based on general clinical disease progression as evaluated by investigator from symptoms/signs of disease, rather than based on a PD according to RECIST 1.1. For the analysis such cases will be handled strictly based on the RECIST 1.1 evaluation, thus if a patient is withdrawn without a CT confirmed PD the subject will be censored at last CT

Analyses will be based on FAS and repeated for separately by strata..

Proportion of Objective Response Rate (ORR) and Disease Control Rate (DCR) from start of sunitinib

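### Primary OS and 18-month survival pool intermediate-risk patients under two sunitinib policies, with no analysis by protocol version, so the result only partly matches the regimen in the OS objective

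*SAP*

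**What the plan says.** **Objectives.** In SAP section 2 (and Protocol 6.1), the OS objective describes vaccination "followed by sunitinib initiated five (5) to eight (8) weeks post-nephrectomy and in non-vaccinated mRCC patients" on the same sunitinib timing. The second objective opens "To evaluate 18-month survival rate from randomization in mRCC patients overall and by subgroup"; it refers to sunitinib after nephrectomy and gives no 5-to-8-week window.

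**Two policies.** SAP 4.1 lists a schedule with sunitinib start 5 to 8 weeks after nephrectomy and then says: "The above described visits are applicable to all randomized subjects after and including protocol version 4.0". Of the earlier design it says: "Following this design intermediate risk subjects would only start sunitinib treatment after confirmed PD". SAP 6.3.6 reports the consequence: "Consequently some patients were never started on sunitinib, and in some cases sunitinib treatment was initiated at a later time point".

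**Handling.** SAP section 1 notes that "prior to protocol version 4.0, the trial design was different for intermediate risk patients, which leads to some specific considerations to be taken". The considerations that follow concern PFS (6.3.6), TTP by reference to PFS, and, in section 5, the other endpoints measured from sunitinib start. The protocol's notes on pre-4.0 patients likewise cover only PFS, response and TTP.

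**Primary analyses.** For OS, SAP 6.3.5 says: "The analyses will be done overall, and separately for high/intermediate risk group of patients". The overall log-rank test is stratified by risk group only. The 18-month comparison (Kaplan-Meier estimates, Greenwood standard errors, z-test) is also run overall and by risk group. The FAS is not divided by protocol version, and the subgroups in SAP 6.8 do not include it.

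**The concern.** The sponsor gives its own reason to think that sunitinib timing could change the vaccine effect. Protocol 7.3 states: "It is anticipated that all patients will benefit more from vaccination with Intuvax the sooner TKI treatment is initiated after performed nephrectomy". If that is right, the intermediate-risk hazard ratio averages the effect with sunitinib at 5 to 8 weeks and the effect with sunitinib deferred to progression or never given. The overall estimate inherits the average.

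Intermediate-risk OS and 18-month survival are named within the primary endpoints, so these are headline results. A weak intermediate-risk result could be read as little vaccine benefit under the regimen in the OS objective, when part of the stratum was never meant to receive that regimen. With no split by version, a reader of the study report could not tell the two explanations apart.

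**Working it through.** The documents give no power, effect size, event count or number of pre-4.0 patients, so there is no stated figure to reproduce. The check has four parts.

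**1. Is the arm comparison still valid?** Timing followed protocol version, not arm. Patients were randomised 2:1 from a separate list per risk group, in sequential blocks (Protocol 9.2). A simulation of the planned risk-stratified log-rank test used 90 patients and no vaccine effect. Its assumptions were 60 intermediate-risk patients, blocks of 6, exponential survival with control medians of 10 months (high risk) and 22 months (intermediate risk), 10% to 50% of the intermediate-risk stratum pre-4.0, and a deferred-versus-early sunitinib hazard ratio of 0.7 or 1.5. Rejection at the two-sided 5% level was 4.8% to 5.8% overall and 5.1% to 5.6% in the intermediate-risk stratum. Pooling does not distort the test of no vaccine effect.

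**2. What does the pooled hazard ratio estimate?** Approximate the pooled log hazard ratio as an event-weighted mean:

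ln HR(pooled) = (1 − f) × ln HR(early) + f × ln HR(deferred)

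Here f is the share of intermediate-risk deaths that come from pre-4.0 patients. All inputs are assumptions: HR(early) = 0.60, f = 0.20, 0.35 or 0.50, and HR(deferred) = 1.00, 0.80 or 0.60. The logarithms are ln 0.60 = −0.511 and ln 0.80 = −0.223.

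| f | deferred 1.00 | deferred 0.80 | deferred 0.60 |
|---|---|---|---|
| 0.20 | exp(−0.409) = 0.66 | exp(−0.453) = 0.64 | 0.60 |
| 0.35 | exp(−0.332) = 0.72 | exp(−0.410) = 0.66 | 0.60 |
| 0.50 | exp(−0.255) = 0.77 | exp(−0.367) = 0.69 | 0.60 |

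The same simulation, run with vaccine hazard ratios of 0.60 (early) and 1.00 (deferred) and a deferred-versus-early ratio of 1.2, shows the same direction. Power in the intermediate-risk stratum falls from 29% with no pre-4.0 patients to 18% at 30% and 11% at 50%.

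**3. Would stratifying the test by version be enough?** No. In that simulation with 30% pre-4.0, overall power was 30.0% with version as an added stratum and 31.3% without. Stratification still gives one averaged effect. Separate estimates are needed.

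**4. Do existing provisions cover the gap?**

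- *PPS (SAP section 5).* The definition requires both vaccine doses (vaccine arm) and nephrectomy. Its exclusion criteria include study medication, sunitinib among it, not given as the protocol defines, but the exact rules are left to the pre-lock deviation review. A pre-4.0 patient who followed the version then in force need not be a deviator, so membership is undetermined.
- *Dose-density Cox model (the SAP text just before 6.3.8).* It covers the primary endpoint and starts with a treatment-by-dose-density interaction. Dose density accumulates after randomisation up to the event or censoring, so it is tied to survival time. Protocol version at inclusion is known at randomisation.

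**The case against.** Several points on the other side stand.

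- **A reader might infer that the primary analyses fail to answer their objective or are biased.** The documents do not support that. Regimen went with version and randomisation was within risk group, so the arm comparison is valid for the sunitinib policies actually used. The 18-month objective has no 5-to-8-week window, and a start deferred to progression is still a start after nephrectomy. Only never-starters clearly depart from its wording. On the documents' account, high-risk results are not affected.
- **A reader might infer that a planned comparison of high-risk with intermediate-risk patients is confounded with regimen.** No such test and no treatment-by-risk interaction is planned; the plan compares arms overall and within each stratum. The problem arises only if the two stratum results are read informally side by side.
- **PFS had a reason for its own rule.** Its time zero is sunitinib start, which is late or undefined for these patients. OS runs from randomisation and is defined for everyone. This explains the asymmetry, but it does not supply the regimen-specific estimate.
- **The size may be small.** Protocol 7.3 expects more benefit with earlier treatment, not none with later treatment. Protocol 5.2 reports objective responses in three of four vaccinated patients given sunitinib after progression. With an assumed 30 to 60 intermediate-risk deaths and 2:1 allocation, the standard error of the log hazard ratio is √(4.5/d), where d is the number of deaths. The 95% interval then extends by a factor of about 2.1 (30 deaths) to 1.7 (60 deaths) either side. That exceeds every shift in the table.
- **All testing is exploratory**, with no power calculation and no multiplicity adjustment (Protocol 12.1.3, SAP 6.4). This limits the weight of the point, but an exploratory estimate still needs a clear target.

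**Conclusion.** The point holds in limited form. In the intermediate-risk stratum, and hence overall, OS and 18-month survival mix two sunitinib policies with no analysis by protocol version. The comparison is randomised and valid for that mixture. It only partly matches the regimen in the OS objective; for 18-month survival the mismatch is clear only for patients who never started sunitinib. Neither the PPS nor the dose-density model replaces a split by version.

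The size cannot be determined from the documents. Under the assumptions shown, a hazard ratio of 0.60 with early sunitinib could appear as anything from 0.60 (equal effects) to 0.77 (no vaccine effect with deferred sunitinib and half of the deaths pre-4.0). That range rests on an unknown pre-4.0 share and on an effect difference that Protocol 7.3 suggests but nothing in the documents measures. This is a worthwhile, inexpensive improvement, not a flaw that invalidates the primary analysis.

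**What to change.** Keep the all-randomised FAS analysis as the main one. In SAP 6.3.5 and 6.8, add the following, labelled exploratory:

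1. The number of intermediate-risk patients included before version 4.0, by arm.
2. Intermediate-risk OS and 18-month survival shown separately for inclusion before version 4.0 and under version 4.0 or later. Classify by version at inclusion, not by whether or when sunitinib was taken, so that each comparison stays randomised.
3. A sensitivity analysis repeating both primary analyses in all high-risk patients plus intermediate-risk patients included under version 4.0 or later.
4. A statement that a side-by-side difference between risk groups will not be attributed to risk alone. This applies in the restricted set too: it keeps early high-risk patients but drops early intermediate-risk ones, so calendar period still differs.

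The cost is SAP wording and a few extra tables, with fewer intermediate-risk patients and wider intervals in the restricted set.
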